5.7.4 Instructions for Initiation of a New Cycle

A new course of treatment may begin on the scheduled Day 1 of a new cycle if:

- The ANC is $\geq 1000/\text{mm}^3$ (G-CSF is allowed to achieve this threshold)
- The platelet count is $\geq 50,000/\text{mm}^3$ (During the first 4 cycles platelet transfusions are allowed to achieve this threshold)
- Any new drug-related neuropathy or rash other than injection site reaction that may have occurred has resolved to \leq grade 1 severity;
- Any bicarbonate decrease below 20mEq/L that may have occurred has resolved to baseline.
- Calculated creatinine clearance $\geq 30\text{ml}/\text{min}$ (by Cockroft-Gault), after 12 cycles on therapy, determining the creatinine clearance every 2 months will suffice
- Any other drug-related adverse events that may have occurred have resolved to \leq grade 2 severity. Physician discretion may be used in initiating the next cycle of treatment if the only toxicities that have not resolved to \leq grade 2 severity are dexamethasone-related toxicities.

If these conditions are not met on Day 1 of a new cycle, the subject will be evaluated weekly and a new cycle of treatment will not be initiated until the toxicity has resolved as described above. If criteria to initiate a new cycle are not met by 21 days after the planned start of a new cycle patients go off study. If a lenalidomide or azacitidine dose reduction was taken during the previous cycle, and the cycle was completed without requiring further dose modification, then the next cycle will start at the same reduced dose. **If lenalidomide and / or azacitidine dosing was omitted for the remainder of the previous cycle or if the new cycle is delayed due to toxicity newly encountered on the scheduled Day 1**, then the new cycle will be started with a one-level dose reduction of lenalidomide and/or azacitidine as appropriate. Dose reductions should generally be taken one drug at a time based on attribution of toxicity to one of the drugs unless otherwise indicated in Section 5.7.3.

5.7.5 Instructions for Dose Modifications or Interruption During a Cycle

Table 5 outlines instructions for dose reductions of study drugs for specific toxicities. Study drugs may be temporarily or permanently dose reduced using doses outlined in table 1-4 or temporarily discontinued in other situations where their continued administration according to protocol is felt unsafe by the treating physician.

Table 5: Dose Modifications Azacitidine and Lenalidomide

NCI CTC Toxicity Grade	Dose Modification Instructions
Grade 3 neutropenia associated with fever (temperature $\geq 38.5^{\circ}$ C) or Grade 4 neutropenia	
 • Hold (interrupt) lenalidomide and, while on combination, also azacitidine dose. • Follow CBC weekly. • During combination therapy with lenalidomide and azacitidine: 
 ◦ If neutropenia has resolved to \leq grade 2 prior to Day 21 of the current cycle, restart azacitidine at the next lower dose level and continue lenalidomide at the same dose level if the patient's myeloma has not previously been refractory to lenalidomide, otherwise maintain azacitidine dose level and reduce lenalidomide by one dose level (if the patient is only on one of these drugs reduce its dose by one level) and continue treatment through the scheduled end of the cycle. Otherwise, omit treatment for the remainder of the cycle and reduce dose levels in the same way at the start of the next cycle. Omitted doses are not made up. ◦ If neutropenia is the only toxicity for which a dose reduction is required (no fever or other reason to reduce doses), G-CSF should be considered instead of a dose reduction. • During maintenance therapy with lenalidomide: 
 ◦ If neutropenia has resolved to \leq grade 2 prior to Day 21 of the current cycle, restart lenalidomide at the next lower dose level, and continue through the scheduled end of the cycle. Otherwise, omit lenalidomide for the remainder of the cycle and reduce lenalidomide by 1 dose level at the start of the next cycle. Omitted doses are not made up.

Table 5: Dose Modifications Azacitidine and Lenalidomide

NCI CTC Toxicity Grade	Dose Modification Instructions
Thrombocytopenia \geqGrade 3 (platelet count $< 50,000/\text{mm}^3$)	
 During the first 4 cycles platelet transfusions may be used at the discretion of the treating physician to achieve platelet counts $\geq 50,000/\text{mm}^3$ on post-transfusion CBCs and thereby maintain the current dose level of lenalidomide and azacitidine. If platelet transfusions are administered, the CBC should be monitored at least twice a week. For thrombocytopenia \geq grade 3 ($< 50,000/\text{mm}^3$) after platelet transfusion or if platelet transfusions are not used hold (interrupt) lenalidomide and, while on combination, also azacitidine dose. If thrombocytopenia \geq grade 4 ($< 25,000/\text{mm}^3$) on a pre-platelet transfusion CBC or if platelet transfusions are not used hold prophylactic anticoagulation Follow CBC weekly, if given platelet transfusions twice a week. If thrombocytopenia resolves to \leq grade 4 ($\geq 25,000/\text{mm}^3$) and last platelet transfusion ≥ 7 days ago resume prophylactic anticoagulation. During combination therapy with lenalidomide and azacitidine: 
 If thrombocytopenia resolves to \leq grade 2 (with or without the use of platelet transfusions) prior to Day 21 of the current cycle, restart azacitidine at the next lower dose level and lenalidomide at the same dose level if the patient's myeloma has not previously been refractory to lenalidomide, otherwise maintain azacitidine dose level and reduce lenalidomide by one dose level (if the patient is only on one of these drugs reduce its dose by one level). Otherwise, omit treatment for remainder of cycle and reduce dose levels in the same way at the start of the next cycle. Omitted doses are not made up. During maintenance therapy with lenalidomide: 
 If thrombocytopenia has resolved to \leq grade 2 prior to Day 21 of the current cycle, restart lenalidomide at the next lower dose level, and continue through the scheduled end of the cycle. Otherwise, omit lenalidomide for the remainder of the cycle and reduce lenalidomide by 1 dose level at the start of the next cycle. Omitted doses are not made up.
Non-blistering rash	
 If Grade 3, hold (interrupt) lenalidomide and, while on combination, also azacitidine dose. Follow weekly. If the toxicity resolves to \leq grade 1 prior to Day 21 of the current cycle, restart lenalidomide at next lower lenalidomide dose level and continue azacitidine at the same dose level through the scheduled end of the cycle. Otherwise, omit treatment for remainder of cycle and reduce the lenalidomide dose by 1 dose level and maintain the current azacitidine dose at the start of the next cycle. Omitted doses are not made up.
Grade 4	
 If Grade 4, discontinue lenalidomide and azacitidine. Remove patient from study.

Table 5: Dose Modifications Azacitidine and Lenalidomide

NCI CTC Toxicity Grade	Dose Modification Instructions
Desquematting (blistering) rash- any Grade	
 Discontinue lenalidomide and azacitidine. Remove patient from study.
Injection site reaction	
 Unless \geq Grade 3 maintain azacitidine dose For Grade 1-2 use post-injection hydrocortisone cream (recommended strength: 2.5%) until resolution. Make sure injection sites are rotated.
Grade 1 (pain, itching, erythema)	
Grade 2 (pain or swelling with inflammation or phlebitis)	
Grade 3 (ulceration or necrosis that is severe, operative intervention indicated)	
 If grade 3 discontinue azacitidine. Remove patient from study.
Neuropathy	
 If Grade 3, hold (interrupt) lenalidomide dose and, while on combination, also azacitidine dose. Follow at least weekly. If the toxicity resolves to \leq grade 1 prior to Day 21 of the current cycle, restart lenalidomide at next lower lenalidomide dose level, restart azacitidine at the current dose and continue treatment through the scheduled end of the cycle. Otherwise, omit treatment for remainder of cycle and reduce the dose of lenalidomide by 1 lenalidomide dose level and maintain the current azacitidine dose at the start of the next cycle. Omitted doses are not made up.
Grade 4	
 If Grade 4, discontinue lenalidomide. Remove patient from study.
Venous thrombosis/embolism \geq Grade 3	
 Hold (interrupt) lenalidomide and start anticoagulation; restart lenalidomide at investigator's discretion (maintain dose level). Omit lenalidomide for remainder of cycle. See Anticoagulation (Section 5.8.1.2)
Hyperthyroidism or hypothyroidism	
 Omit lenalidomide for remainder of cycle, evaluate etiology, and initiate appropriate therapy. See Instructions for Initiation of a New Cycle and reduce the dose of lenalidomide by 1 lenalidomide dose level.
Bicarbonate - low (CO₂ below 20mEq/L)	
 If unexplained hold azacitidine and lenalidomide Check weekly Upon recovery to baseline restart azacitidine at next lower dose level and restart lenalidomide at the current dose. If recovery to baseline occurs prior to Day 21 of the current cycle, restart as instructed above and continue treatment through the scheduled end of the cycle. Otherwise, omit treatment for remainder of cycle and reduce the dose of azacitidine by 1 dose level and maintain the current dose of lenalidomide at the start of the next cycle. Omitted doses are not made up.

Table 5: Dose Modifications Azacitidine and Lenalidomide

NCI CTC Toxicity Grade	Dose Modification Instructions
Renal impairment (Calculated creatinine clearance \geq 30ml/min < 60ml/min)	
 Maintain current dosing schedule, but reduce lenalidomide by 1 dose level (see Section 5.7.1, Table 2). If lenalidomide dose had been \geq 15mg, reduce to 10mg daily on Days 1-21 of each 28-day cycle.
(Calculated creatinine clearance < 30ml/min)	
 Hold lenalidomide and, while on combination, also azacitidine Check weekly Upon recovery to calculated creatinine clearance \geq 30ml/min restart at next lower dose level for both lenalidomide and azacitidine (see Section 5.7.1, Table 2 and Table 3). If lenalidomide dose had been \geq 15mg, reduce to 10mg daily on Days 1-21 of each 28-day cycle. If recovery occurs prior to Day 21 of the current cycle, restart as instructed above and continue treatment through the scheduled end of the cycle. Otherwise, omit treatment for remainder of cycle and reduce the dose of azacitidine by 1 dose level and reduce the dose of lenalidomide by 1 dose level at the start of the next cycle (see Section 5.7.1, Table 2 and Table 3). If lenalidomide dose had been \geq 15mg, reduce to 10mg daily on Days 1-21 of each 28-day cycle. Omitted doses are not made up.
other non-hematologic toxicity \geq Grade 3	
 In general hold (interrupt) lenalidomide and, while on combination, also azacitidine dose but clinical discretion may be used to only hold the most likely causative agent. Follow at least weekly. If the toxicity resolves to \leq grade 2 prior to Day 21 of the current cycle, restart lenalidomide and azacitidine and continue through the scheduled end of the cycle. Otherwise, omit treatment for remainder of cycle. Omitted doses are not made up. For toxicity attributed to lenalidomide, reduce the lenalidomide dose by 1 lenalidomide dose level when restarting lenalidomide. For toxicities attributed to azacitidine, reduce dose by one azacitidine dose level when restarting azacitidine.

Table 6: Dose Modifications Dexamethasone

NCI CTC Toxicity Grade	Dose Modification Instructions
Dyspepsia Grade 1-2	
 Maintain dose Add proton pump inhibitor or H2 blocker
Dyspepsia Grade > 3	
 Hold dose Add proton pump inhibitor or H2 blocker When symptoms controlled decrease one dose level and restart. Omitted doses are not made up
Edema \geq Grade 3	
 Use diuretics as needed and decrease by one dose level
Confusion or mood alteration \geq Grade 2	
 Hold dose until symptoms resolve. When restarting decrease one dose level.
Muscle weakness (steroid myopathy) \geq Grade 2	
 Hold dose until muscle weakness < Grade 1. When restarting decrease one dose level.
Hyperglycemia \geq Grade 3	
 Decrease dose by one dose level. Treat with insulin or oral hypoglycemic agent.
Acute pancreatitis	
 Discontinue dexamethasone

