5.8.1.2 Anticoagulation

Lenalidomide increases the risk of thrombotic events in patients who are at high risk or with a history a thrombosis, in particular when combined with other drugs known to cause thrombosis. When lenalidomide is combined with other agents such as steroids

(e.g. dexamethasone, prednisone), anthracyclines (Doxil, Adriamycin) and erythropoietin the risk of thrombosis is increased.

Prophylactic anticoagulation is mandatory on this trial according to guidelines outlined under 5.6.2.5 with holding and restarting parameters as per Table 5 (hold for plts < 25,000/mm³, restart once plts \geq 25,000/mm³ and platelet transfusion independent for > 7 days).

In case of documented deep venous thrombosis or embolism standard anticoagulation with subcutaneous low molecular weight heparin or intravenous heparin with conversion to warfarin will be started. Full anticoagulation will be maintained for at least 12 months while patients are on lenalidomide and at least 6 months if they have gone off trial and the DVT was below the knee (distal to the popliteal vein).

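### Table 5's thrombosis row gives two lenalidomide instructions that cannot both be followed in a cycle, and section 5.7.4 points to a different restart dose level

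*Combined protocol and SAP*

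**What the plan says.** **Thrombosis row (section 5.7.5, Table 5).** For venous thrombosis or embolism of grade 3 or higher, lenalidomide is interrupted and anticoagulation started. Restart is at the investigator's "discretion (maintain dose level"). The next sentence reads "Omit lenalidomide for remainder of cycle", followed by a pointer to section 5.8.1.2.

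**New-cycle rule (section 5.7.4).** Where lenalidomide and/or azacitidine was left out for the rest of the previous cycle, "then the new cycle will be started with a one-level dose reduction of lenalidomide and/or azacitidine as appropriate". The section adds that reductions should generally be taken one drug at a time, by attribution.

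**Thrombocytopenia row (section 5.7.5, Table 5).** Prophylactic anticoagulation is held at grade 4 or above, given as a count below 25,000/mm³. The restart bullet begins "If thrombocytopenia resolves to", names grade 4 or below, gives a count of at least 25,000/mm³, requires the last platelet transfusion to be at least 7 days back, and ends "days ago resume prophylactic anticoagulation".

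**Section 5.8.1.2.** Prophylaxis is mandatory, "with holding and restarting parameters as per Table 5". The restated parameters are: hold below 25,000/mm³, and restart at 25,000/mm³ or more when "platelet transfusion independent for > 7 days".

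**The concern.** Table 5 is what an investigator consults when a patient has a thrombosis, and for lenalidomide it gives two consecutive instructions that do not fit together. The trial runs at two institutions with small dose cohorts, so two investigators could treat the same event differently without either departing from the protocol. Lenalidomide exposure would then vary within a dose level for a reason that the safety report by dose level would not show.

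The platelet wording is a lesser matter. A grade label disagrees with the number beside it, and a section that says it follows Table 5 states a slightly different interval.

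**Working it through.** The plan gives no figure to reproduce here. The check sets the rules side by side, then sizes the dose difference from Tables 1 and 2.

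**1. After a thrombosis, same cycle.** The first sentence of the row permits a restart at the investigator's discretion. The second requires omission until the cycle ends. As an illustration only, a restart on day 8 leaves up to 21 − 8 + 1 = 14 of the 21 scheduled daily doses; omission leaves none.

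**2. After a thrombosis, next cycle.** Suppose the row means omit for this cycle and restart in the next at the maintained level. The omission then meets the trigger in section 5.7.4, which starts the new cycle one level lower, as appropriate. The row says same level and section 5.7.4 says one level down. Neither passage refers to the other, and no text ranks them.

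**3. Size of one level, from the starting doses.**

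| Source | Dose kept | One level lower | Ratio |
|---|---|---|---|
| Table 1 | 25 mg × 21 days = 525 mg | 20 mg × 21 days = 420 mg | 420/525 = 80% |
| Table 2 | 10 mg × 21 days = 210 mg | 15 mg × 11 doses = 165 mg | 165/210 = 79% |

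The difference is 20% by Table 1 and about 21% by Table 2. The 11 doses assume dosing every 48 hours on days 1, 3, …, 21. As a plain daily average, 15 mg every 48 hours is 7.5 mg/day against 10 mg/day, a 25% difference, but that ignores the 21-day window. The Table 2 line also assumes that patients enrolled at 10 mg for reduced GFR follow Table 2, since Table 1 excludes toxicities in the presence of renal impairment. For patients already reduced, later Table 1 steps are larger: 20 to 15 mg is 25%, 15 to 10 mg is 33%, and 10 to 5 mg is 50%.

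**4. Restart of prophylactic anticoagulation.**

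| Situation | Table 5, grade label | Table 5, count | Section 5.8.1.2 |
|---|---|---|---|
| Below 25,000/mm³, more than 7 days since transfusion | restart | hold | hold |
| At least 25,000/mm³, exactly 7 days since transfusion | restart | restart | do not restart yet |
| At least 25,000/mm³, more than 7 days since transfusion | restart | restart | restart |

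The label disagrees with the count in the first line only. The two sections disagree in the second line only.

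**The case against.** **On the thrombosis row.** Section 5.7.4 is qualified by its closing words and by the preference for reducing one drug at a time. Table 5 also shows that omission does not mean reducing every omitted drug: the rash and neuropathy rows stop both drugs and keep the azacitidine dose, and the bicarbonate row stops both and keeps the lenalidomide dose. On this view, keeping the lenalidomide level after a thrombosis is simply what is appropriate. That softens the conflict with section 5.7.4 but does not settle it. Those rows state each drug's dose for the next cycle, and each reduces the other drug. The thyroid row refers to the new-cycle instructions and states the reduction. The thrombosis row does neither, and lenalidomide is the only drug it stops. Nor does the qualification touch the clash between the row's own two sentences.

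**On bleeding risk.** A reader might infer that the plan lets anticoagulation restart at counts where it must be held. The documents do not support this. The count of 25,000/mm³ is printed beside the label, and section 5.8.1.2 repeats it with no grade attached. The label looks like a slip next to a clear number. The interval difference matters only on the seventh day after a transfusion.

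**On dose-limiting toxicity.** Section 5.1 exempts grade 3 or 4 thromboembolism provided anticoagulant therapy can be given, so a reader might infer that these conflicts affect the DLT count. The platelet row concerns prophylactic anticoagulation, not treatment of a thrombosis, so it does not decide that exemption. The dose difference sized above falls in the next cycle; for an event in cycle 1, that is after the 28-day DLT window. The same-cycle ambiguity can alter lenalidomide exposure in cycle 1, but nothing in the documents shows that a DLT count or the highest tolerated low dose would change.

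**Conclusion.** The point holds for the thrombosis row. Its two lenalidomide instructions cannot both be followed within a cycle. The reading that reconciles them meets the section 5.7.4 trigger for a reduction that the row itself does not make. From the starting doses, the next cycle differs by one level, roughly 20%: 25 against 20 mg daily, or 210 against about 165 mg per cycle. The second pair rests on the 11-dose assumption and on Table 2 applying to patients enrolled at 10 mg.

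The platelet mismatches are real but secondary: one grade label against its own count, and at least 7 against more than 7 days. They show no conflict over when lenalidomide itself resumes after low platelets, although a reader might infer one because the same row covers both drugs and prophylaxis. Nothing here changes a sample size, an error rate, the DLT definition or the determination of the highest tolerated low dose.

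**What to change.** Reword the thrombosis row of Table 5 so that it gives one instruction for lenalidomide within the cycle and one for the dose level at the next cycle. State in that row or in section 5.7.4 which of the two governs. In the thrombocytopenia row, make the grade label agree with its count, and use one transfusion-free interval in Table 5 and section 5.8.1.2. Which clinical rule applies in each place is for the sponsor's clinicians.

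The cost is a few lines of amendment text in Table 5 and sections 5.7.4 and 5.8.1.2, with a memo to the two sites. No analysis or sample size needs to be redone.

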5.7.6 Treatment Compliance

Research center personnel will review the dosing instructions with subjects. Subjects will be asked to maintain a diary to record the drug administration (appendix VII). Subjects will be asked to bring any unused drug and empty drug containers to the research center at their next visit. Research personnel will count and record the number of used and unused drug at each visit and reconcile with the patient diary. Azacitidine will be administered at the Taussig Cancer Center and at University Hospital Ireland cancer Center, compliance will be assessed by review of medication administration reports. Any unused Revlimid® (lenalidomide) should be returned to the patient for disposition in accordance with the RevAssist® program.

5.8 Concomitant Therapy

5.8.1 Recommended Concomitant Therapy

Subjects should receive full supportive care, including transfusions of blood and blood products, antibiotics, and antiemetics when appropriate.

5.8.1.2 Anticoagulation

Lenalidomide increases the risk of thrombotic events in patients who are at high risk or with a history a thrombosis, in particular when combined with other drugs known to cause thrombosis. When lenalidomide is combined with other agents such as steroids

(e.g. dexamethasone, prednisone), anthracyclines (Doxil, Adriamycin) and erythropoietin the risk of thrombosis is increased.

Prophylactic anticoagulation is mandatory on this trial according to guidelines outlined under 5.6.2.5 with holding and restarting parameters as per Table 5 (hold for plts < 25,000/mm³, restart once plts \geq 25,000/mm³ and platelet transfusion independent for > 7 days).

In case of documented deep venous thrombosis or embolism standard anticoagulation with subcutaneous low molecular weight heparin or intravenous heparin with conversion to warfarin will be started. Full anticoagulation will be maintained for at least 12 months while patients are on lenalidomide and at least 6 months if they have gone off trial and the DVT was below the knee (distal to the popliteal vein).

5.8.1.3 Concomitant Therapy with Azacitidine

5HT3 serotonin receptor antagonists should be administered at least 30min prior to each azacitidine dose. If constipation or headache limits the use of HT3 antagonists, metoclopramide may be used.

Rotation of azacitidine injection sites is obligatory. Patients who nevertheless experience grade 1-2 injection site reactions should be treated with topical hydrocortisone (2.5% cream recommended) until resolution.

5.8.2 Prohibited Concomitant Therapy

Concomitant use of other anti-cancer therapies, thalidomide, or other investigational agents is not permitted while subjects are receiving protocol therapy on this study. Palliative radiation (with the exception of pelvic radiation) is permitted.

5.9 Discontinuation of Study Treatment Including Progressive Disease Definition

Treatment will be discontinued in case of:

- Progressive Disease (see under 5.9.1)
- Adverse event(s) that, in the judgment of the Investigator, may cause severe or permanent harm or which rule out continuation of the treatment regimen.
- Delay of the start of a new cycle by more than 21 days due insufficient recovery from toxicity
- Permanent discontinuation of lenalidomide for any reason
- Major violation of the study protocol
- Withdrawal of consent
- Lost to follow up
- Death
- Suspected pregnancy or positive pregnancy

